#### 17.3.2 Planned recruitment rate

NeoART aims to randomize 200 participants in total. We have faced challenges meeting our recruitment target in. We have therefore discussed these issues with the DMC and TSC in the UK and a decision has been made to combine the data from the UK with a mirror study in Vietnam (NeoART-Vietnam) and Malaysia (NeoART-Malaysia). Although different study populations, these are mirror studies in terms of trial protocol, study procedures and Investigational Medicinal Product source. The target recruitment in the UK will now be 34, Vietnam will be 46 and Malaysia will be 120 patients and a target trial recruitment of 200 patients.

In Malaysia, 5 Ministry Of Health, Universiti Malaya are ready to open the trial. We aim to recruit 8-12 participants to the study per month in each sites in Malaysia over 24 months.

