#### 7. Trial design

#### 7.1 Overall Design

This study is a Phase II, randomised, double blind, placebo controlled, multi-centre trial. We aim to recruit 200 patients presenting with stage II/III colorectal cancer.. Patients who consent to enter the study will receive the trial intervention for 2 weeks prior to their planned surgery and then be followed up for 5 years following surgery.

A master randomisation list generated by the Sponsor representative was made available at the start of the study. The master randomisation list is further divided into blocks of 20 and provided to each study site with the IMP deliveries. The Research Pharmacy or CRC at each site will retain the randomisation list upon receipt in their Pharmacy Site File. Upon receipt of a NeoART prescription the next sequential allocation will indicate whether to dispense active artesunate or matched placebo tablets to a particular participant. At the time of

dispensing the tear off label identifying the product will be removed by the Research Pharmacy or CRC and added to the accountability log. This will ensure that the investigators and study participants remain blinded to the treatment allocation. In exceptional circumstances, when knowledge of the investigational drug is essential for medical treatment of the patient, treatment allocation can be unmasked by pharmacy or CRC centres by a study coordinator that is not involved in the study directly .

The Sponsor retain a copy of the master randomisation list in their respective study files.

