# 17.3 Sample size and recruitment

#### 17.3.1 Sample size calculation

We performed our sample size calculation largely based on inferences drawn from our pilot Phase I study (Krishna *et al.*, 2015). The input assumes that the analysis would be conducted using a univariate Cox proportional hazard survival model from the time of surgery to the first disease recurrence with one binary covariate representing treatment groups (artesunate or placebo). We calculated that a minimum sample size of 168 patients is necessary to test a hazard ratio (HR) of 0.56 for the intervention versus placebo. This value is within the confidence intervals estimated in our phase I study (Krishna *et al.*, 2015) and somewhat between the point estimate in the worse case scenario inference in the paper and a value of 0.7 commonly circulated in oncology clinical trials. For this Phase II study, we set the power at 0.8 and accepted a type one error of 0.1 for a one-sided test.

- 1) The null nypothesis H0: HR=0.56 (equivalent ≤)
- 2) The alternative hypothesis H1: HR>0.56

These settings would result in a sample size of 168 patients. Inflating this sample size by 15-20% to allow for loss at follow-up would result in approximately 194-202 patients. We believe that 200 patients therefor represents a feasible and achievable target given our time and financial constraints.

The rationale and sensitivity analyses for these calculations are outlined below. The general setting is that of a survival analysis where the event is defined as the first disease recurrence after surgery.

A cohort of Stage II/III colorectal cancer patients undergoing surgery will be randomised as per recruitment to receive the artesunate intervention or placebo. Patients will be followed-up for 5 years following surgery. The minimum sample size to test a hazard ratio (HR) of 0.56 for the intervention vs. placebo group is based on:

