#### Calculation framework:

- 1. The minimum sample size calculation has been calculated as for a univariate Cox proportional hazard survival model with one binary covariate representing treatment groups (artesunate or placebo).
- 2. The necessary number of events are calculated as

[figure not shown]
$$D = (Z_{1-\alpha} + Z_{1-\beta})^{2} \left[ P \times (1 - P) \times (\log(HR))^{2} \right]^{-1}$$

Where P represents the proportion of the sample assigned to the treatment group (0.5 corresponding to a 1:1 treatment assignment in our setting) and the HR is the estimated hazard ratio of the event (disease recurrence) for the treatment group vs. placebo. The values of the inverse of the standard normal cumulative distribution function are

 $Z_{1-\alpha}=1.28$  for one sided  $\alpha$ =0.1 and  $Z_{1-\beta}=0.842$  for  $\beta$ =0.20 (equivalent to 80% power).

3. Hence, the minimum total number needed for the trial is calculated as

$$N = D \times (100/32)$$

Graph 1: Study sample size- a sensitivity analysis to various settings for hazard ratios and type one error for one-sided test.

Total number	One sided level of	HR	Number of events
participants	significance		
53	.15	4	17
56	.15	.4 .41	18
59	.15	.41	19
62	.15	.42	20
66	.15	.43	22
70	.15	.45	23
74	.15	.46	24
78	.15	.47	25
82	.15	.48	27
87	.15	.49	28
92	.15	.5	30
104	.15	.52	34
117	.15	.54	38
132	.15	.56	43
149	.15	.58	48
169	.15	.6	55
193	.15	.62	62
222	.15	.64	72
256	.15	.66	82
297	.15	.68	96
347	.15	.7	112
68	.1	.4	22
71	.1	.41	23
75	.1	.42	24
80	.1	.43	26
84	.1	.44	27
89	.1	.45	29
94	.1	.46	31
99	.1	.47	32
105	.1	.48	34
111	.1	.49	36
118	.1	.5	38
132	.1	.52	43
149	.1	.54	48
168	.1	.56	54
190	.1	.58	61
216	.1	.6	70
247	.1	.62	80
283	.1	.64	91
327	.1	.66	105
379	.1	.68	122
443	.1	.7	142
93	.05	.4	30
98	.05	.41	32
103	.05	.42	33
109	.05	.43	35
115	.05	.44	37
122	.05	.45	40
129	.05	.46	42
136 144	.05	.47	44
152	.05	.48 .49	47 49
	.05 .05	.5	52
161			
181	.05	.52	58
204	.05 .05	.54	66 74
230		.56	
261	.05 .05	.58	84
207	U.S.	.6	96
297			100
339	.05	.62	109
			109 125 144

608	.05	.7	195

Table 2: Details sensitivity analyses to various settings for hazard ratio values. Power is set at 0.8.

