The inference is expressed in survival type metrics: i.e. proportion of individuals surviving recurrence beyond 1 year, 2 years and median time to recurrence in each group. Predictions (survival prognostics) will refer to the colon cancer population within our data range.

Missing data (attrition) will be assessed and sensitivity analysis will be employed upon the particularities exhibited by the data, i.e. missing data pattern and whether the missing information is associated with the main outcome. This will include data analysis under a 'missing at random assumption' and imputation methods tailored to interval censored data will also be applied.

Both a frequentist and Bayesian framework for statistical inference are envisaged. The uncertainty will be expressed in terms of 95% confidence intervals (CI) or 95% credible intervals (CrI) for their corresponding estimates. The frequentist statistical significance would be deemed at the 0.05 (5%) level.

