## 17.4 Randomisation

Patients recruited to the study will be randomised to receive either artesunate or placebo in equal proportions. Randomisation lists will be generated for each site by computer-generated code, supplied by the study Sponsor's representative to the Clinical Trials Pharmacist or a study coordinator who is not part of the investigator's team only. The code will only be broken in exceptional

circumstances, when knowledge of the investigational drug is essential for medical treatment of the patient.

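### Three country studies with different populations are pooled, but the primary Cox model names no country stratum; the likely loss is small and the remedy nearly free

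*Protocol*

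**What the plan says.** - **Pooling.** Protocol 17.3.2 merges three country studies with targets of 34 (UK), 46 (Vietnam) and 120 (Malaysia), 200 in all. It says: "Although different study populations, these are mirror studies in terms of trial protocol, study procedures and Investigational Medicinal Product source".
- **Sizing model.** Section 17.3.1 states that a "minimum sample size of 168 patients is necessary to test a hazard ratio (HR) of 0.56 for the intervention versus placebo", and "we set the power at 0.8 and accepted a type one error of 0.1 for a one-sided test". The calculation framework rests on a "univariate Cox proportional hazard survival model with one binary covariate representing treatment groups (artesunate or placebo"), with allocation of "0.5 corresponding to a 1:1 treatment assignment in our setting". It uses one event share, 0.32 (7/22), from the pilot.
- **Analysis model.** Sections 17.3.3 and 17.3.3.1 describe a Cox model comparing artesunate with placebo, with follow-up censored at 2 years. They name no country or site term and no stratum. Section 8.6 says that adjuvant treatment after surgery will be brought into the final analysis.
- **Lists.** Section 17.4: "Randomisation lists will be generated for each site by computer-generated code". Section 7.1: "The master randomisation list is further divided into blocks of 20 and provided to each study site with the IMP deliveries".

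**The concern.** The multi-country design was written into 17.3.2, but the statistical sections still read as for one population with one event rate. Two things follow.

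First, the Cox hazard ratio is not collapsible. If baseline recurrence differs between countries and country is left out, the pooled hazard ratio lies nearer 1 than the ratio within each country, even with perfect randomisation. Where lists are balanced within site, ignoring that balance also makes the standard error slightly too large, so part of the allowed type I error goes unused.

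Second, 7.1 and 17.4 describe different ways of making the lists. Separate site lists can be balanced within site. A single master list cut into portions of 20 is balanced within site only if each portion is itself a permuted block, which the protocol does not state. Without that, chance imbalance of the arms by country adds noise to an unstratified estimate.

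What is at stake is a little precision and power, and having the handling of country settled before Malaysian outcomes accrue.

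**Working it through.** **1. The plan's own figure.** With P = 0.5, Z values 1.28 and 0.842, and HR 0.56:

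D = (1.28 + 0.842)² / [0.25 × (ln 0.56)²] = 53.6, so 54 events. N = 53.6 × 100/32, about 167.5, so 168. Both match 17.3.1.

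Power at 54 events is Φ(|ln 0.56| × √(54/4) − 1.28) = Φ(2.13 − 1.28) = 80.2%.

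**2. Large-sample attenuation.** Country rates are my assumption, since the documents give none. I took a constant hazard λ within each country, HR 0.56 in every country, weights w of 34/46/120, censoring at 2 years, and the overall event share held at 0.32. For arm a (0 placebo, 1 artesunate):

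- S_a(t) = Σ w exp(−λ·0.56^a·t)
- f_a(t) = Σ w λ·0.56^a exp(−λ·0.56^a·t)

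The unstratified log hazard ratio β solves ∫₀² [f₁ − (f₀ + f₁)·S₁e^β/(S₀ + S₁e^β)] dt = 0. The result goes back into the formulas of step 1.

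| Placebo 2-year recurrence, UK/Vietnam/Malaysia (%) | Unstratified HR | Power at 54 events (%) | Events needed | N |
|---|---|---|---|---|
| 39.5/39.5/39.5 | 0.560 | 80.2 | 54 | 168 |
| 30.0/41.4/41.4 | 0.561 | 80.0 | 54 | 169 |
| 24.2/42.5/42.5 | 0.563 | 79.7 | 55 | 171 |
| 17.5/43.8/43.8 | 0.565 | 79.2 | 56 | 174 |
| 20.4/59.9/36.6 | 0.571 | 78.1 | 58 | 180 |
| 69.7/32.8/32.8 | 0.576 | 77.3 | 60 | 185 |

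This formula uses the same standard error with and without strata. With lists balanced within country that overstates the spread of the unstratified estimate, so the simulation below is the better guide to power.

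**3. Simulation.** N = 200, true HR 0.56, exponential recurrence, 2-year censoring, no dropout, one-sided 10%. There were 10,000 trials per pattern for the first four rows and 3,000 for the rest (simulation error at 3,000 about √(0.84 × 0.16/3000) = 0.7 points). Ranges show repeat runs.

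| Placebo rates (%) | Lists within country | HR, unstratified vs stratified | Power (%), unstratified vs stratified |
|---|---|---|---|
| 39.6/39.6/39.6 | balanced | 0.558 vs 0.559 | 84.9 vs 84.9 |
| 25/42/42 | balanced | 0.561 vs 0.558 | 83.6 vs 83.6 |
| 20/45/40 | balanced | 0.565 vs 0.560 | 82.4 vs 82.7 |
| 20/60/38 | balanced | 0.571 vs 0.559 | 84.5 vs 85.5 |
| 15/30/50 | balanced | 0.57 vs 0.56 | 83 vs 84-85 |
| 15/30/50 | simple allocation | 0.57 vs 0.56 | 83 vs 84-85 |
| 10/30/60 | balanced | 0.58 vs 0.55-0.56 | 87 vs 88-89 |
| 10/30/60 | simple allocation | 0.58 vs 0.55-0.56 | 84-85 vs 88 |

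With the UK at 60% and the other two at 30%, power is 80-81% against 81% (balanced) and 79% against 81% (simple).

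**4. Type I error.** With HR 1 and balanced lists, the unstratified test rejected in 9.3-10.2% of trials under the four patterns in the first rows, and in as few as 7-9% under the wider ones, against a nominal 10%. Nothing exceeded 10% beyond simulation error.

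**5. What country-level estimates could show.** At an event share of 0.32, the UK gives 34 × 0.32 ≈ 11 events and Vietnam 46 × 0.32 ≈ 15. The standard error of the log hazard ratio is about 2/√11 = 0.60 and 2/√15 = 0.52. A hazard ratio of 0.56 would then carry 95% limits of roughly 0.17-1.83 in the UK and 0.20-1.54 in Vietnam.

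**The case against.** The strongest reply is that the protocol does not fix a treatment-only analysis. The one-covariate model is an input to the sample size. The analysis text lists no covariates but excludes none, 8.6 promises to include adjuvant therapy, and strata are often left to a statistical analysis plan, which is not shown here. This stands as a limit: a reader might infer that the primary analysis is fixed with treatment alone, and the text does not go that far. It does not dispose of the point. Section 17.3.1 says the sizing anticipates that analysis, the protocol carries its own analysis-plan section, and that section leaves out a population difference which 17.3.2 openly admits.

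The second reply is size, and it also stands. Rates of 15% and 50% imply a hazard gap of ln 0.50/ln 0.85 = 4.3-fold, and 10% and 60% a gap of ln 0.40/ln 0.90 = 8.7-fold, all under one Stage II/III eligibility definition. The 10/30/60 pattern also gives an overall event share of about 0.37, not 0.32. The largest losses further need simple allocation, which neither 7.1 nor 17.4 describes. Portions of 20 may well be balanced blocks; the text does not say.

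Three other inferences are tempting and unsupported:

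- **That country confounds the comparison.** Allocation is 1:1, and the test stays valid.
- **That pooling will cause a visible failure of proportional hazards and a change of model under 17.6.** Under 15/30/50 the pooled hazard ratio drifts only from 0.56 to 0.59 over 2 years, and under 10/30/60 to 0.62. Section 17.6 calls its own statements speculative.
- **That UK and Vietnam outcomes have already been analysed.** Sections 17.3.3 and 17.5 say that a December 2021 look was discussed, not that it took place.

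**Conclusion.** The point holds as an inexpensive improvement, not as a validity failure. The protocol pools three populations that it calls different and randomises by site, but names no country stratum in its primary Cox model.

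If recurrence differs by country, the unstratified hazard ratio moves from 0.56 to about 0.56-0.58. Power falls by about 0-2 points with balanced lists, and by about 3-4 points only with unbalanced lists and extreme rates. Type I error is not inflated. A reader might infer that country differences will materially dilute the effect; the calculation does not support that.

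These sizes rest on assumed country rates, constant hazards, a common hazard ratio of 0.56 and the design's one-sided 10%. Section 17.3.3.1 states a different level ("The frequentist statistical significance would be deemed at the 0.05 (5%) level"). That conflict is a separate matter; it would change the power figures but not the attenuation.

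The two accounts of list generation need reconciling whatever the analysis plan says.

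**What to change.** 1. **Sections 17.3.3 and 17.3.3.1:** state that the primary Cox model is stratified by country (UK, Vietnam, Malaysia) and estimates one common treatment hazard ratio. Use the same strata for overall and cancer-specific survival in 17.3.3.3.
2. **Country results:** present hazard ratios by country with confidence intervals, as description only. With about 11 UK and 15 Vietnam events, an interaction test could neither confirm nor refute the claim that these are mirror studies, so none should be relied on.
3. **Sections 7.1 and 17.4:** give one account of how the lists are made, and say that each Malaysian site's list is balanced 1:1 within blocks.

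Cost: a sentence or two of analysis wording and a check of the Malaysian lists. Country is known for every patient. If recurrence is equal across countries, the loss of information is negligible (simulated power 84.9% with or without strata). The sample size need not change.

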# 17.3.3 Statistical analysis plan

The event of interest (failure defined as cancer recurrence from a survival analysis perspective) is defined as the first recurrence of the disease after the patients' treatment allocation and surgery. Patients will be followed-up for 2 years; if the event of interest does not occur the patient will be considered (right) censored. The general assumption for time-to-event (survival analysis) is that the censoring is non-informative, i.e. it is independent of the event process. The Cox proportional hazard (PH) model would be applied to investigate the hazard ratio of disease recurrence for the artesunate group versus placebo group. The semi-parametric technique allows no assumption to be made on the baseline hazard; nevertheless proportionality of the hazards in the two arms should hold. The latter assumption can be tested on the basis of Shoenfeld residuals after fitting the model to the data.

We discussed an interim analysis in December 2021 with the DMC and TSC. At this time point 78 patients will have reached the primary end point (recurrence free survival 2 years after surgery). This analysis will be performed by an independent trial statistician familiar with both trials ([name]) and a report presented to the DMC and TSC members for review and recommendations thereafter.

#### 17.3.3.1 Summary of baseline data and flow of patients

Details of the number of patients eligible for the trial, the number of patients consenting and the number randomised along with a breakdown for each group of the numbers of participants assigned, receiving the intended treatment, completing the study protocol, and analysed for the primary outcome will be clearly documented. This information will be displayed as a flow diagram (http://www.consort-statement.org/).

The analyses will be performed in STATA (StataCorp. 2014. Stata Statistical Software: Release 14. College Station, TX: StataCorp LP.) and/or (R: A language and environment for statistical computing. R Foundation for Statistical Computing, Vienna, Austria. ISBN 3-900051-07-0, URL http://www.R-project.org/). GraphPad (Prism) or other comparable statistical package.

Descriptive statistics, preliminary analysis and graphics will be used to understand the data structure, the nature of the variables and the appropriateness of the subsequent tests and analyses. Data will be summarized as mean, standard deviation and range if normally distributed. If the data are skewed then additional statistics such as median and inter-quartile ranges will be used to correctly describe the selected sample in the population. Parametric or non-parametric tests will be used as appropriate to ensure/verify that the two groups do not differ statistically with respect to any aspects but the intervention.

Three safety interim analyses are planned as the trial data collection proceeds, approximately after 10%, 50% and 75% of patients have completed their day 28 assessments.

The appropriate statistical framework for the analysis of the primary outcome is that of a survival analysis. Patients will be followed-up up to 2 years; if the event of interest does not occur within this time frame, the patient is considered (right) censored. The general assumption is that the censoring is independent of the event process. The Cox proportional hazard (PH) model would be applied to investigate the hazard ratio of disease reccurrence for the artesunate group vs. placebo group. The semi-parametric technique allows no assumption to be made on the baseline hazard; nevertheless proportionality of the hazards in the two arms should hold. The latter assumption can be tested on the basis of Shoenfeld residuals after fitting the model to the data.

The inference is expressed in survival type metrics: i.e. proportion of individuals surviving recurrence beyond 1 year, 2 years and median time to recurrence in each group. Predictions (survival prognostics) will refer to the colon cancer population within our data range.

Missing data (attrition) will be assessed and sensitivity analysis will be employed upon the particularities exhibited by the data, i.e. missing data pattern and whether the missing information is associated with the main outcome. This will include data analysis under a 'missing at random assumption' and imputation methods tailored to interval censored data will also be applied.

Both a frequentist and Bayesian framework for statistical inference are envisaged. The uncertainty will be expressed in terms of 95% confidence intervals (CI) or 95% credible intervals (CrI) for their corresponding estimates. The frequentist statistical significance would be deemed at the 0.05 (5%) level.

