#### 11.2 Randomisation procedure

Participants recruited to the study will be randomised to receive either artesunate or placebo 1:1. Randomisation will be by a computer-generated code. An unblinded randomisation list will be provided to each participating site and held in Pharmacy or held by a study coordinator that is not directly involved in the study. Following completion of the study the participant treatment allocation list held in the site Pharmacy files will be anonymised prior to collection by the Clinical Trials Monitor. The anonymised lists will be handed over to the statistician to facilitate data analysis.

All patients will be given a study specific 24 hrs emergency contact card immediately after being randomised. The card includes details of the Trial: Study title, details of IMP, patient trial number, CI/PI's contact details along with out of hours contact details in case of emergency.

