#### 17.2 Endpoints

## 17.2.1 Primary endpoints

The primary endpoint for the main comparison between the artesunate treatment and placebo arms will be persistent disease or disease recurrence, two years following surgery. All analyses will be made on an intention to treat basis, although per protocol analyses will also be reported. Statistical significance will be assumed at the 5% level unless otherwise indicated.

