The minimum sample size has been calculated within the same general circumstances and similar outcome (disease recurrence) as the pilot study. Namely, the calculations are initially based on the HR of treatment group versus placebo group values ranging from 0.15-0.31 as obtained in our pilot study (assuming a 1:1 randomization). The overall ratio of events (disease recurrence) was 0.32 (7/22). However, given the small sample size of the pilot study, we have extended our sensitivity analysis up to the value of 0.56 for the hazard ratio and the corresponding sample size to 200 patients (see graph 1 and table 2). May we add that, under the assumption that the intervention is not worse, the numbers would also be valid for a setting in which one-sided alpha level of significance is set at 0.15 and HR = 0.6 and for one sided alpha level of significance of 0.05 and HR = 0.5 – with power held at 0.8.

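### The trial is sized for a one-sided 10% test but judged at 5%, so the stated 80% power is really about 57% (two-sided) or 69% (one-sided)

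*Protocol*

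**What the plan says.** Three places in the protocol set an error level that bears on the primary comparison.

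- **Section 17.3.1 (sample size calculation):** "For this Phase II study, we set the power at 0.8 and accepted a type one error of 0.1 for a one-sided test". On that basis, "We calculated that a minimum sample size of 168 patients is necessary to test a hazard ratio (HR) of 0.56 for the intervention versus placebo". The calculation framework in the same section uses a normal quantile of 1.28 and reports 54 events, and the total is then inflated to about 200 for loss to follow-up.
- **Section 17.2.1 (primary endpoints):** "Statistical significance will be assumed at the 5% level unless otherwise indicated". Sidedness is not given.
- **Section 17.3.3.1:** after the Cox model for the primary outcome and the handling of missing data, the text says "The uncertainty will be expressed in terms of 95% confidence intervals (CI) or 95% credible intervals (CrI) for their corresponding estimates", and then "The frequentist statistical significance would be deemed at the 0.05 (5%) level". Sidedness is again not given, and there is no qualifier.

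Section 17.3.3.2, which is headed as the primary endpoint analysis, states no level. No analysis section repeats the one-sided 10% level.

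**The concern.** Power is a property of a particular test at a particular level. Here the design calculation uses one level and the text that governs inference uses a stricter one. The 80% shown to funders, ethics committees and the DMC then does not describe the test that will be reported.

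There is also a problem of pre-specification. Some results would meet the one-sided 10% criterion and miss the 5% criterion. With both levels in the protocol, either could be cited after unblinding, and the choice would decide whether the trial is called positive.

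**Working it through.** **Inputs, all from the protocol.** Hazard ratio 0.56, power 0.80, one-sided alpha 0.10 (section 17.3.1); 1:1 allocation, so P = 0.5 (section 11.2); event proportion 0.32, from 7/22 in the pilot (section 17.3.1); target 200 patients. The null is taken as a hazard ratio of 1, which is what the protocol's formula implies.

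**Step 1. Reproduce the stated figure.** The protocol uses D = (z_α + z_β)² / [P(1−P)(ln HR)²].

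- ln 0.56 = −0.5798, so the denominator is 0.25 × 0.3362 = 0.0840.
- One-sided 0.10: (1.2816 + 0.8416)² / 0.0840 = 53.6, rounded up to 54 events.
- N = 53.6 / 0.32 = 167.6, rounded up to 168 patients.

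Both match the protocol.

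**Step 2. Same formula at the level in the analysis text.**

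| Test | D | Events | Patients before loss (D/0.32) |
|---|---|---|---|
| One-sided 0.10 | 53.6 | 54 | 168 |
| One-sided 0.05 | 73.6 | 74 | 230 |
| Two-sided 0.05 | 93.4 | 94 | 292 |

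The second row is also printed in the protocol's own sensitivity table (230 patients, 74 events).

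**Step 3. Power with the planned events.** Power = Φ(√(D/4) × 0.5798 − z_α). For D = 54 the first term is 3.674 × 0.5798 = 2.130. For D = 64 (all 200 patients followed without loss, 200 × 0.32) it is 4 × 0.5798 = 2.319.

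| Test | z_α | Power, 54 events | Power, 64 events |
|---|---|---|---|
| One-sided 0.10 | 1.282 | 80.2% | 85.0% |
| One-sided 0.05 | 1.645 | 68.6% | 75.0% |
| Two-sided 0.05 | 1.960 | 56.8% | 64.0% |

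At 5%, neither sidedness reaches 80%, even with no loss at all.

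**Step 4. Results on which the two rules disagree.** The critical observed hazard ratio is exp(−z_α × 2/√D). With 54 events, 2/√54 = 0.2722.

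- One-sided 0.10: exp(−1.282 × 0.2722) = 0.706.
- One-sided 0.05: exp(−1.645 × 0.2722) = 0.639.
- Two-sided 0.05: exp(−1.960 × 0.2722) = 0.587.

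If the true hazard ratio is 0.56, the chance of a result that passes at one-sided 10% and fails at 5% is the difference in power: 80.2 − 56.8 = 23% for the two-sided test and 80.2 − 68.6 = 12% for the one-sided test.

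**Step 5. Effect that 54 events can detect with 80% power.** HR = exp(−(z_α + z_β)/√(54/4)): 0.561 at one-sided 0.10, 0.508 at one-sided 0.05 and 0.467 at two-sided 0.05.

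**The case against.** The best defence is that 5% is only a default. The sentence in section 17.2.1 allows for exceptions ("Statistical significance will be assumed at the 5% level unless otherwise indicated"), and section 17.3.1 can be read as one. Section 17.3.3.1 is headed as a summary of baseline data and patient flow, so its 5% could be a general reporting convention. Reporting 95% intervals does not by itself contradict a one-sided 10% test. This would be a coherent plan if the text said so. But section 17.3.3.1 repeats 5% with no exception, in the text that follows the primary Cox model, and section 17.3.1 says what error was accepted for sizing without saying that the final test will use it.

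A second defence is that section 17.3.1 says the numbers also hold at one-sided 0.05. They do, but only for a hazard ratio of 0.5 (161 patients and 52 events in the table). That is a larger effect than the 0.56 on which the trial is justified, and nothing is offered for a two-sided 5% test.

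A third point stands in part. Neither 5% statement gives sidedness, and all the sizing is one-sided, so 57% is one of two readings. It is the one that matches a 95% interval; on the other reading power is 69%. Both fall short of 80%.

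A relaxed alpha is usual in phase II and is not criticised here. The fault is sizing on one level and declaring significance on another.

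**Conclusion.** The concern holds. The sample size is correctly derived for a one-sided 10% test, but the analysis text fixes 5%. At that level the planned 54 events give 56.8% power (two-sided) or 68.6% (one-sided) for a hazard ratio of 0.56, not 80%. These figures rest on the protocol's own formula, proportional hazards, 1:1 allocation, a null hazard ratio of 1 and 54 observed events. The base of 54 is appropriate because the increase to 200 patients is an allowance for loss. This must be settled before unblinding, since it can decide how the trial is reported.

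**What to change.** State one level and one sidedness for the primary comparison in sections 17.2.1, 17.3.1 and 17.3.3.1. There are two ways to do it.

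1. **Keep the design level.** Say in 17.2.1 and 17.3.3.1 that the primary comparison is tested one-sided at alpha 0.10, with the matching two-sided 80% confidence interval. The 95% interval can stay as descriptive, and 5% can stay for the other analyses.
2. **Keep 5%.** State the sidedness and correct 17.3.1. Power at a hazard ratio of 0.56 is then about 57% (two-sided) or 69% (one-sided). Equivalently, 80% power holds only for a hazard ratio of about 0.47 (two-sided) or 0.51 (one-sided).

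Either is a change of wording and needs no more patients; under the second, the stated power becomes less favourable. Keeping both 5% and 80% power at 0.56 would need 230 patients (one-sided) or 292 (two-sided) before any allowance for loss.

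Two neighbouring texts should be checked in the same edit so that the chosen level attaches to the right test: the null and alternative hypotheses written in 17.3.1, which are set around 0.56 and not 1, and the interim look at primary-endpoint data in 17.3.3 and 17.5.
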